Brain and Genetic Predictors of Individual
Differences in Pain and Analgesia
(Pain Genetics)

NCT03781570

Study Protocol

4/11/2023

TITLE: Brain and Genetic Predictors of Individual Differences in Pain and Placebo Analgesia

PROTOCOL VERSION DATE: 11 April 2023

VERSION: 16

PRINCIPAL INVESTIGATOR (PI):

Name: [name]

Address: Institute for Behavioral Genetics, [name]

[contact]

Email: [contact]

KEY PERSONNEL

Name: [name]

Role in project: Research Coordinator

Name: [name]

Role in project: Co-Investigator

Name: [name]

Role in project: Co-Investigator

Name: [name], Dartmouth College

Role in project: Co-Investigator

Name: [name]

Role in project: Co-investigator

Name: [name], Dartmouth College

Role in project: Research Coordinator

Name: [name]

Role in project: Research Coordinator

Name: [name]

Role in project: Research Coordinator

I. OBJECTIVES

The goal of this study is to characterize the neurophysiological mechanisms that make an individual a strong or weak placebo responder, and provide behavioral and genetic markers for these individual differences. This would provide a tool for characterizing likely placebo responders in clinical settings and clinical trials, with two benefits. First, it could be used to better separate placebo vs. verum treatment effects, allowing for better targeting of the mechanisms of each type of effect. Second, it could be used to eliminate or control for placebo responses in clinical trials, increasing efficiency and trial success rates.

II. BACKGROUND AND SIGNIFICANCE

Throughout history, placebo effects have been variously considered as tricks played upon the gullible by medical practitioners and powerful but mysterious healing forces. With the advent of direct measurements of human brain function, modern science has shown that placebo effects are neither of these. Rather, they reflect the principled impact of psychological and brain processes on diseases of the brain and body. Placebo effects represent an opportunity because they provide a window into internal brain processes that influence health, and a challenge because many clinical trials have now failed due to large and durable placebo responses, at great cost to health care providers and consumers.

Definitive studies of the brain pathways involved in placebo responses—and the genetic, environmental, and neural factors that lead some individuals to respond more strongly than others—are critical to harnessing placebo effects, eliminating or controlling placebo responses in clinical trials, and understanding the psychological and brain factors that predispose one to successful treatment and “spontaneous” improvement. Placebo analgesia is the best-studied type of placebo effect, with well-developed paradigms and preliminary data on its brain mechanisms. This background provides a foundation for larger-scale, definitive studies.

In this project, we propose the first such large-scale study of brain mechanisms of placebo analgesia, combining neuroimaging, behavioral, and genetic approaches. It builds on 15 years' experience in PI [name]'s laboratory on fMRI and placebo analgesia and 40 years of genetics research at the Institute for Behavior Genetics (IBG) at the University of Colorado, Boulder. We will use fMRI to characterize the neural bases of placebo effects in 600 twins recruited from the Colorado Twin Sample and predict individual differences in placebo effects across two forms of pain. In **Aim 1**, we will develop models that predict the magnitude of individuals' placebo effects in pain and pain neurophysiology based on a) fMRI activity, b) brain structure, and a combination of personality, behavioral, and cognitive measures that can be deployed clinically. In **Aim 2**, we conduct the first analyses of heritability of placebo effects and their neural predictors, and genetic correlations that can identify brain features whose relationships with placebo effects are genetic in origin. In **Aim 3**, we leverage the >50,000 person Enhancing Neuro-Imaging

Genetics through Meta-analysis (ENIGMA) consortium to identify genome-wide associations with placebo-linked brain features and develop polygenic risk scores for placebo effects. The research products from this endeavor will include data and models useful for characterizing and screening participants in clinical trials, assessing interactions between placebo responses and other treatments, and assessing placebo effects across disorders.

III. PRELIMINARY STUDIES

Large placebo responses occur in clinical trials of multiple mental health and neurological disorders, including Parkinson's¹⁻³, autism⁴⁻⁷, epilepsy⁸, schizophrenia^{9,10}, migraine¹¹⁻¹³, other forms of chronic pain¹⁴⁻¹⁷, and other brain disorders¹⁸⁻²¹. Fifteen years of research on brain mechanisms of placebo by our lab and others has found that placebo effects are reliably caused by *active neurobiological processes* that must be studied and understood in relation to health and disease^{20, 22-26}. Placebo analgesia is the best studied area, but evidence suggests mechanistic overlap with placebo effects in Parkinson's disease²⁷⁻³⁰ and depression³¹⁻³⁵. These include prefrontal-striatal-brainstem interactions and involvement of endogenous neurochemicals (opioids, dopamine, cannabinoids, serotonin, and others) that may form a common substrate for influences of affective systems and context across disorders²²⁻²⁴. Understanding the neuroscience of placebo is a key to understanding endogenous brain contributions to disease vulnerability and resilience, and maximizing clinical benefit. It is also a key to increasing success rates in clinical trials. A growing number of trials are failing because of large placebo responses^{9, 16, 18, 36}, with large economic and public health costs. The ability to eliminate or control for placebo responses in clinical trials would help bring successful drugs to market.

IV. RESEARCH STUDY DESIGN

[figure not shown]

A.2.1. Behavioral assessments. Before the main neuroimaging session, participants will complete a battery of online behavioral measures, including measures of (a) personality and (b) cognitive control (Fig. 3). At a six to twelve-month follow-up, participants will be contacted to complete a series of tasks, including tasks that measure (a) perceptual/decision biases and (b) affective biases. **Personality and affective state measures** include those with previous relationships with placebo effects in smaller studies (reviewed above), particularly the Life Optimism Test Revised (LOT-R³⁸¹), Behavioral Inhibition/Behavioral Activation (BIS/BAS³⁸²), State/Trait Anxiety Inventory (STAI^{59, 240, 383}), Beck Depression Inventory (BDI³⁸⁴), Fear of Pain (FOP³⁸⁵), Ego Resilience (ER-89³⁸⁶), and the “Big 5” brief inventory (neuroticism, openness, agreeableness, extraversion, conscientiousness³⁸⁷).

Perceptual/decision bias tasks are adaptations of sensory suggestibility tasks predictive of placebo effects in past studies³⁸⁸⁻³⁹⁰. A series of perceptual judgments are made of the color, size, etc. of visible objects, and the test assesses whether judgments are biased by the identities of the objects. **Affective bias measures** use a well-validated task that assesses whether individuals consistently identify ambiguous faces and images as positive or negative in valence^{390, 391}. **Cognitive control measures** include tasks studied extensively by our group³⁹²⁻³⁹⁵, including measures of cognitive flexibility (letter/number

task switching), response selection (go/no go, stop-signal, and antisaccade), and working memory (N-back and keep-track tasks). These tasks will be administered online in the month before scanning through the study website (www.paingen.science) in which all data will be stored in the secure RedCap system³⁹⁶, with reaction time-based tasks implemented using Javascript embedding. Prior data collection waves on the CTS sample include neuroticism and extroversion³⁹⁷, reward-dependence³⁹⁸, harm-avoidance³⁹⁸ and behavioral disinhibition³⁹⁹, and standardized cognitive tests (PIAT-R, WISC-III), which we will also correlate with placebo outcomes. In order to test functionality and gather preliminary data for these online measures, we will recruit a pilot sample of 1000 ‘online only’ participants using Amazon’s Mechanical turk system. The link for mturk participants will be: www.paingen.science/mtruk.

An additional behavioral assessment titled ‘Skin Prick Test (Allergy test)’ will be administered after the fMRI tasks on the day of testing at the Center for Innovation and Creativity (CINC). This task is modeled after previous research done in the Stanford Psychology department (Howe, Grover, Crum, 2017) in which 164 participants received the skin prick test with no adverse side effects. All subjects who are cleared for this task (based on a short in person screening procedure on the day of testing: see attachment ‘skin prick test screening and allergy task instruction’ document) will participate after the

fMRI scanning procedures. The allergy test will involve participants experiencing an induced itch through a standardized 'skin prick test' involving administration of a drop of 1mg/ml histamine gel (1% histamine dihydrochloride in 2.5% methylcellulose). Skin prick tests involving histamine are used as controls in routine allergy diagnosis tests. Typical allergy tests are done with actual (food or environmental) allergens. However, we will not be using any allergens in this procedure. Histamine is an organic compound naturally produced by the body and is classified as a monoamine neurotransmitter.

This test has been used in numerous studies to induce itching (e.g., Bromm, Scharein, Darsow, & Ring, 1995; Darsow, Ring, Scharein, & Bromm, 1996; Pfaff et al., 2006, 2010). Further, this procedure induces an itching sensation, but did not cause pain or any other sensations to any participants in previous studies. Histamine will be applied to two skin sites on the participant's non-dominant volar forearm. Two inert creams will be administered to the participant with the suggestion that one will 'decrease the allergic reaction and itching' and the other will 'increase the allergic reaction and itching' (counterbalanced between subjects). Allergic reactions or 'wheals' will be measured for 30 minutes after application. This task is designed to measure participant's placebo response(s) in a non-painful scenario. This will allow us to compare different types of placebo responses, expectations, and genetic factors that contribute to the placebo effect.

A.2.2. fMRI study design. The design of the proposed fMRI experiment is based closely on our work on fMRI of placebo analgesia over the last 15 years^{221, 400-409}, including recent studies comparing intensity-matched thermal and mechanical pain ($N = 81$ fMRI subjects run to date). There are two main phases during fMRI: In the placebo administration phase, participants are given two identical creams with different instructions: "Procaine, an effective pain-relieving drug" (Placebo) and "a control cream with no effects" (Control) applied to 4 fingers each on the left hand, with locations counterbalanced across subjects. Disclosure of side effects are presented on forms with realistic-looking drug company logos (see attachment 'drug_info_packet_script_PAIN-GEN'), and testing is done in a medical environment with medical equipment and related context cues. A 2-minute delay follows for the "cream to take effect", during which we will ask the participant to complete the survey "side effects questionnaire". Structural (T1-weighted) images will be collected prior to any of the placebo tests. A post-conditioning test phase tests both pain types on and off placebo treatment after reinforcement. We have successfully used similar procedures⁴¹⁴, as have others²²² (e.g., C. Büchel, $N = 700$ with suggestion-alone and post-conditioning, no imaging) Rating scale: Ratings of pain intensity and unpleasantness will be made after each trial on a 100-point generalized visual analogue scale⁴¹⁵⁻⁴¹⁸ with anchors of "no pain" or "no unpleasantness" and "most intense sensation imaginable," or "Most unpleasantness imaginable", using an fMRI-compatible trackball²²¹.

Stimulation and trial details. A Control-Placebo-Control design (e.g., ^{222, 414}) in each stimulation phase permits assessments of placebo effects within individuals, without confounding placebo with habituation (or sensitization) to pain and avoiding order effects. Based on prior work, we expect little to no habituation of pain responses with this protocol^{221, 288, 414, 419, 420}. Each trial will consist of: (1) A warning cue, followed by a variable-duration anticipation interval (4-16 sec with exponential distribution, 6 sec mean ^{73, 221}); (2) thermal or mechanical pain (10 sec plateau with 2 sec ramp up/down); (3) a 4-16 sec jittered delay followed by rating scales (4 sec each); (4) a 4-16 sec inter-trial interval. Ramps minimize head movement during stimulation to very low levels (0.07 mm average³⁷). Standard stimulus intensities will permit assessment of individual differences in brain and behavior holding objective stimulus intensity constant^{144, 421}. Based on previous calibration studies in our lab (heat $N = 495$, pressure $N = 81$), we will select heat and pressure intensities matched for pain in the

population. Max “high pain” intensities of 49° C and 7 kg/cm² are expected to be “very painful” for ~83% of the sample but tolerable for nearly all (98%) of participants^{144, 270, 421}. A variable-duration anticipation period separates anticipatory activity from stimulus processing.

For the thermal stimuli, the temperatures will range from 43 to 49 °C, and the pressure will range from 4 to 7 kg/cm². As part of the screening process, we will perform a pain calibration procedure with the thermode (Medoc, Inc.) on each participant in order to ensure that all temperatures delivered during any subsequent procedures are within participants’ tolerable range. Pain stimulation will be performed using a contact thermode (Medoc, Inc.) that is placed against the skin. The thermode is actively heated and cooled by the hardware of the device. Temperature values are controlled to within .1 degrees Celsius by a computer, with a safety shutoff at a level tolerable to some participants, and nondamaging to skin (the hardware will not allow stimulation at 50 degrees Celsius for longer than 6 seconds). Stimulation will not exceed 50 degrees Celsius in any of the studies covered under this protocol unless explicitly noted in a separate protocol.

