Aim 1: Analyses 1a-1c identify brain and psychological predictors of placebo analgesia, respectively. Placebo effects will be defined as Control vs. Placebo ([C – P]) differences in pain report (“placebo analgesia”) and two validated, pain-related brain measures: the NPS and SIIPS. These analyses will allow us to identify common and differential brain predictors of placebo effects on behavioral (pain report)

and neurobiological outcomes. They will permit three other novel tests: (1) Whether predictive patterns generalize across thermal and mechanical pain; (2) Whether they generalize across placebo effects in suggestion alone or post-conditioning; and (3) Whether we can identify latent factors across outcomes (thermal/mechanical, suggestion/conditioning), and develop predictors of those domain-general outcomes. Such factors are more likely to be genetically determined and useful in broader clinical contexts.

Multiple comparisons and power:

This study is the first large-scale study powered for *whole-brain analyses* of structural and functional correlates of placebo analgesia with Family-Wise Error Rate (FWER) map-wise correction. We will use FWER correction as implemented in Statistical Nonparametric Mapping (SnPM)⁴²³. This correction is valid, makes minimal assumptions, and is not affected by recent findings of inflated false positive rates with some correction methods⁴²⁴. With our sample size ($N = 600$), we have 80% power with whole-brain FWER correction to detect correlations with placebo analgesia of $r \geq 0.22$, which is within the range of our previous cross-validated estimates^{37, 268, 269, 353, 354, 369}.

Previous studies have been substantially underpowered; with $N = 50$, which is larger than most placebo studies, correlations must be $r = 0.65$ or larger to be detectable with 80% power. Though this is the first study adequately powered for whole-brain correction, we will also focus on testing hypotheses derived from the previous literature, as described below.

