- 13. Skin Prick Task/Allergy test (see ‘skin prick testing procedures and allergy task instructions’ for details of procedure):** Prior to the start of this task, participant will fill out the document: ‘skin prick test screening’ to ask about any criteria that would exclude them from this task. If the participant marks any of these questions with an ‘X’, they will be excluded from this task. Although the ‘skin prick test screening’ asks about regular intake of antihistamine medication, we will not exclude participants from the allergy test if they indicate any allergies or regular intake of anti-allergy medication. This information regarding allergies, will be documented and referred to if necessary. The experimenter will conduct a blood pressure test to check for excessively high/low blood pressure. Only participants who fall within the normal blood pressure range will be eligible for this task. Participants with excessively high (over 150 Systolic and over 100 Diastolic) or low (Under 80 Systolic and under 60 Diastolic) will be excluded from the test. These are the blood pressure levels appropriate for testing as advised by the allergist. The histamine gel is applied to the skin on the lower left arm and skin is punctured superficially using a standard blood lancet (UniTest PC produced by Lincoln Diagnostics; Decatur, IL). The UniTest PC testing system includes three parts: 1) the blood lancet used for delivering the prick, 2) a reservoir filled with the appropriate allergen (in this case histamine gel) and 3) a tray containing 40 sterile pouches for storing the reservoirs (for more details see attachment: ‘ Dipwell_instructions’ and ‘unit-pc-ad’ pdf). Reservoirs will be filled with 12 drops of histamine gel and stored in the trays. The UniTest PC blood lancets are then placed individually in each reservoir and stored in a refrigerator at 2-8 degrees Celsius. When the allergy test needs to be conducted, the researcher will first swab the forearm site with an alcohol wipe and allow to dry. Then, they will take a single use UniTest PC blood lancet out of the tray (loaded with histamine) and prick one site on the participant’s forearm. The UniTest PC prick lancets will be applied with medium pressure to the skin site in order to apply the histamine gel. Researchers will follow the UniTest PC instructions as well as training from an allergist (see ‘Allergist training instructions’). This process will be repeated with a new UniTest PC blood lancet for the other site on the forearm (two total sites pricked using two different blood lancets). The blood lancets will be disposed of in a sharps container after the allergy test. Two inert creams will be administered to the participant with the suggestion that one will ‘decrease the allergic reaction and itching’ and the other will ‘increase the allergic reaction

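### The itch task has no neutral reference, so its within-person contrast is placebo plus nocebo and should not be reported as a placebo response; antihistamine users stay in without an analysis rule

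*Protocol*

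**What the plan says.** Protocol section IV, A.2.1 gives the purpose of the skin prick task: "This task is designed to measure participant's placebo response(s) in a non-painful scenario". It then states the intended use: "This will allow us to compare different types of placebo responses, expectations, and genetic factors that contribute to the placebo effect".

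On the design, the same section says: "Histamine will be applied to two skin sites on the participant's non-dominant volar forearm". One inert cream comes with "the suggestion that one will 'decrease the allergic reaction and itching"; the other is said to "increase the allergic reaction and itching' (counterbalanced between subjects". Section XI, item 13 confirms that two sites are pricked in all. It lists itch ratings at 3, 6, 9, 12 and 15 minutes, all after histamine.

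The pain tasks use a different reference. In section IV, A.2.2 the comparison cream is described to participants as having no effects. Section IV, A.3 (Aim 1) then says: "Placebo effects will be defined as Control vs. Placebo", for pain report and two brain measures (NPS and SIIPS).

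On medication, section XI, item 13 says: "we will not exclude participants from the allergy test if they indicate any allergies or regular intake of anti-allergy medication". The allergy information is to be recorded and consulted as needed. The instrument table in section XI shows that the intro survey also records medications.

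Neither the protocol nor the SAP defines an itch score, a model for it or a medication adjustment.

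**The concern.** The study sets out to identify strong and weak placebo responders. In the itch task both conditions carry an active suggestion, in opposite directions. Someone who responds only to the negative suggestion can get the same score as someone who responds only to the positive one.

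If that score is called a placebo response and related to pain placebo or to genetic factors, a positive finding could reflect nocebo. A null finding could reflect nocebo variation hiding a real placebo link.

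The medication point is separate. The stimulus is histamine, so a drug that blocks its action can flatten both sites and pull the difference towards zero for reasons unrelated to expectation.

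**Working it through.** The documents give no effect size, sample size or formula for the itch task, so there is no figure to reproduce. The main step is structural; the numbers after it are illustrations.

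**1. The contrast.** Let D and I be a participant's reaction under the decrease and increase suggestions, and N the reaction under a neutral cream, which is never observed. Write p = N − D (placebo part) and n = I − N (nocebo part). Then

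S = I − D = (N − D) + (I − N) = p + n.

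N cancels, so no analysis of D and I recovers p or n. For example, p = 2, n = 0 and p = 0, n = 2 both give S = 2. Counterbalancing the creams deals with differences between sites but does not supply N. The pain contrast, Control minus Placebo, has the form of p.

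**2. How well S tracks p.** With k = SD(n)/SD(p) and ρ = corr(p, n), both assumed,

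corr(S, p) = (1 + ρk) / √(1 + k² + 2ρk).

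| k | ρ = −0.3 | ρ = 0 | ρ = 0.3 | ρ = 0.5 | ρ = 0.8 |
|---|---|---|---|---|---|
| 0.5 | 0.87 | 0.89 | 0.92 | 0.94 | 0.98 |
| 1 | 0.59 | 0.71 | 0.81 | 0.87 | 0.95 |
| 2 | 0.21 | 0.45 | 0.64 | 0.76 | 0.91 |

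The range is 0.21 to 0.98, and the design cannot show where in it the study lies.

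**3. Correlation with pain placebo.** Let r_p and r_n be the correlations of pain placebo with p and with n. For independent components of equal variance (k = 1, ρ = 0), the observed correlation is (r_p + r_n)/√2. With r_p = 0.40:

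- r_n = 0: 0.40/1.414 = 0.28
- r_n = 0.17: 0.57/1.414 = 0.40
- r_n = 0.40: 0.80/1.414 = 0.57

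The observed value can fall below, match or exceed the true one, depending on r_n, which the documents do not give.

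**4. Antihistamine users.** If a share q has no reaction at either site, the mean contrast becomes (1 − q) of its value among reactors: 0.95 at q = 5%, 0.80 at q = 20%. If their response is only halved, it is (1 − q) + 0.5q, or 0.90 at q = 20%. The documents give neither q nor the degree of suppression.

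**5. Screening text.** Section XI, item 13 says that any screening item marked with an X excludes the person from this task. It then says that allergies and regular anti-allergy medication do not exclude, although the form asks about antihistamines. The two sentences conflict as written.

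**The case against.** **The task is peripheral.** It is an additional assessment, absent from Table 1, from the Analysis 1c measures, from the heritability and genetic-correlation models and from the SAP. A.2.1 speaks loosely of placebo responses of different types and never equates the itch score with the pain contrast. This stands and limits the importance of the point. It does not remove it, because A.2.1 still states a purpose and a use that the design cannot support, and nothing elsewhere qualifies them.

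**The pain contrast is not purely neutral either.** Under A.2.2, conditioning pairs the Control and Placebo sites with different intensities before the test phase (section XI, item 7 words the pairing in the opposite order, which must be reconciled). Both pain creams therefore carry learned expectations, and the itch task has no conditioning. This stands: even a neutral second itch cream would not make the two tasks equivalent.

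**The score may still work well.** If placebo and nocebo responses are strongly and positively correlated, S follows p closely (0.91 to 0.98 at ρ = 0.8 above). That is possible, but this design cannot test it.

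**Antihistamines favour neither cream.** They would be expected to act at both sites, and use is recorded, so adjustment remains possible. This stands; what is missing is a planned rule.

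**Conclusion.** The concern holds in a limited form. The itch contrast is a combined placebo-nocebo score, and this follows from the two-site, two-suggestion design without further assumptions. Conclusions about pain-itch agreement or shared genetic factors therefore cannot be attributed to placebo alone. The size and direction of any bias are unknown.

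A reader might infer more than the documents support:

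- *That 0.28 is a ceiling on the observed correlation.* It is the value at r_n = 0 only. A shared responsiveness to suggestion would make r_n positive and raise it.
- *That the itch effect is overstated against the pain effect.* If mean placebo and nocebo shifts were equal, the contrast would be twice the placebo part. However, pain is rated on a 100-point scale while itch uses separate ratings and ruler-measured wheals, and no comparison of effect size across them is planned.
- *That antihistamine use shrinks the contrast by a known amount or distorts twin similarity.* The documents give no prevalence, no degree of suppression and nothing on sharing of allergy within pairs.
- *That the main result is at risk.* The SAP's main analysis concerns thermal pain ratings and does not use the itch task.

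**What to change.** 1. In Protocol section IV, A.2.1, define the itch and wheal outcomes as a decrease-versus-increase suggestion difference. Do not report them as a placebo response equivalent to Control minus Placebo. State that comparisons with pain placebo and with genetic factors use a combined placebo-nocebo score.
2. Prespecify itch and wheal results with and without participants who have recorded regular antihistamine use. The protocol already collects this information.
3. Reconcile the two screening sentences in section XI, item 13.

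Two further changes may look attractive but should be avoided. Excluding participants with no wheal selects on an outcome measured after the suggestion, which the suggestion is meant to change. Rewording the second cream mid-study would create two versions of the task that cannot simply be pooled, could split twin pairs between them, and would lose the existing contrast.

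The cost is protocol wording and one sensitivity analysis on data already planned, with a narrower claim for the task and a smaller set in that sensitivity analysis.
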